#### **16.0 STATISTICAL CONSIDERATIONS AND METHODOLOGY**

#### 16.1 Study Design

#### **16.1.1 Study Populations**

A total of 177 premenopausal women will be pre-registered, among which 96 patients with atypia (Masood Score 14-17) on RPFNA at baseline are expected to be randomized between

Metformin arm and placebo control arm. It is expected that the accrual rate will be 1 patient per month and that accrual will be completed about 8 years after study activation. The randomization will be stratified for known BRCA mutation (BRCA1 or BRCA2 mutation vs. no mutation), prior excisional biopsy (atypical epithelial hyperplasia, atypical lobular hyperplasia, flat epithelial hyperplasia vs. DCIS vs. LCIS), and baseline fasting insulin > 2x ULN vs.  $\leq 2x$  ULN.

At 12 months the women in the placebo arm will be allowed to take metformin. Based on experience from 300 women undergoing serial RPFNA at Duke, it is anticipated that approximately 40% of women who are randomized to the metformin arm will have disappearance of atypia at 12 months and 60% will have persistent atypia. The estimated drop-out rate is 5% at 6 months and 10% at 12 months. Over 98% of women with atypia will have atypia on repeat RPFNA on the non-metformin arm.

We propose to test RPFNA on both right and left breasts at, 12 and 24 months after registration/randomization for the presence or absence (Masood score  $\leq$ 13) of atypia by Masood Cytology Index Score. The RPFNA at 24 months is optional for women who continue on the placebo control arm and will not receive metformin. The outcomes collected at 24 months will be exploratory. In analysis, we will consider taking a transformation, such as logarithm, of positive variables in order to improve the normality and variance stabilization. Among the 96 randomized patients, we expect that about 10% of patients will drop out at month 12. So, the power analyses are based on N= 88 patients (44 per arm).

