#### Alliance A211102

In another exploratory analysis, we will compare the continuous Masood score between two arms. The sampling unit in this analysis will be breast. The change rate (ratio) in Masood score at month 12 from baseline will be compared between metformin group and placebo control group using two-sample t-test for univariate analysis with 2-sided alpha=5%. We will also conduct multivariate analysis to regress the month 12 Masood score on group indicator, age, race, prior excisional biopsy, and baseline Masood score.

Since the sampling unit in this analysis is breast, the Masood score observations from two breasts may be potentially correlated. In order to account for possible dependency between the data points from two breasts of each woman, the variances of t-test (in univariate analysis) and regression estimates (in multivariate analysis) will be estimated using the GEE.

It is expected that about 25% of women (n = 11) will contribute one breast and the remaining 75% of women (n = 33) will contribute samples from both breasts, so that there will be about 77 (= 11x1 + 33x2) data points (breasts) per arm in this analysis. Assuming that the intracluster correlation coefficient between two breasts is 0.3, this analysis will have 84% power to detect a difference of 0.4 times the standard deviation (SD).

Similar analyses will be conducted for 24 months data.

The women or breasts with unsatisfactory repeat RPFNAs will be considered missing at random in the analysis.

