#### 16.2.2 Secondary Objectives:

# 16.2.2.1 Test for Masood score and the presence of atypia or disappearance of atypia in RPFNA after 12 (for both arms) and 24 months for Metformin arm:

We will investigate the trend of Masood score and presence of atypia measured at month 0 and 12 for metformin arm and placebo arm. Breasts will be the sampling units in the analysis of Masood score, while either women (in the primary analysis) or breasts (in the secondary analysis) will be regarded as sampling units in the analysis of atypia. At first, we will perform descriptive analyses for summary statistics of Masood score and atypia at each measurement time. We will also generate a line plot connecting the Masood scores of each breast over time to investigate the time trend.

We will compare the mean Masood scores between 0 vs. month 12 using paired ttests. In this analysis, we will use the breasts as sampling units. The possible dependency between data points from two breasts of each woman will be adjusted using the GEE method using the working independent correlation model. Assuming that about 25% of women (n=11) will contribute one breast and the remaining 75% of women (n=33) will contribute samples from both breasts for each arm, we will have 90% of statistical power to detect a difference of 0.3 times SD if the intracluster correlation coefficients between breasts and two time points are 0.3 for each woman. We will conduct McNemar test to compare the proportion of atypia between month 0 and month 12. These analyses will be conducted for each arm, and the results will be descriptively compared between two arms. We will summarize the 24-month data for the metformin arm.

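### Two power statements for the breast-level Masood score analyses do not follow from the plan's inputs: 84% between arms computes to about 60%, and 90% within an arm to about 48–65%

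*Combined protocol and SAP*

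**What the plan says.** Section 16.1.1 removes dropout first: "the power analyses are based on N= 88 patients (44 per arm"). Both power statements use the same split per arm: 11 women contribute one breast and 33 contribute two, so 77 breasts.

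- **Section 16.2.1.2, between arms (exploratory).** The ratio of month-12 to baseline Masood score is compared "using two-sample t-test for univariate analysis with 2-sided alpha=5" per cent, with variances from GEE to allow for two breasts per woman. A second model will "regress the month 12 Masood score on group indicator, age, race, prior excisional biopsy, and baseline Masood score". With an intracluster correlation of 0.3 between breasts, the plan states that "this analysis will have 84% power to detect a difference of 0.4 times the standard deviation (SD"). It does not say which SD.
- **Section 16.2.2.1, within arm (secondary).** Month 0 and month 12 mean scores are compared by paired t-test with breasts as units. On clustering: "The possible dependency between data points from two breasts of each woman will be adjusted using the GEE method", using working independence. The power claim is "we will have 90% of statistical power to detect a difference of 0.3 times SD". It is made on one stated condition about correlation, namely "if the intracluster correlation coefficients between breasts and two time points are 0.3 for each woman". On pooling: "These analyses will be conducted for each arm, and the results will be descriptively compared between two arms". No alpha is given here, the SD is not defined, and no separate value is given for the correlation between one breast at month 0 and the other at month 12.

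**The concern.** With 77 correlated breasts per arm, 84% power for 0.4 SD and 90% for 0.3 SD both look too high. Clustering inflates the variance, yet the stated powers exceed what 77 fully independent breasts would give.

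These two statements are the plan's power figures for the continuous Masood score, and the second supports a secondary objective. A non-significant result would be read against a claimed 16% or 10% chance of missing the effect. If the true chance is several times larger, a null result could be taken as evidence of no effect when the analysis was not able to show one.

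**Working it through.** Normal approximation throughout; two-sided 5% (z = 1.960) unless stated. The two-sided level is given in 16.2.1.2 and is assumed for 16.2.2.1.

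**Variance of an arm mean.** Under working independence, with m breasts per woman and correlation ρ, variance = Σ m[1 + (m − 1)ρ] / (Σ m)², in SD² units. With 11 women at m = 1, 33 at m = 2 and ρ = 0.3:

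(77 + 66 × 0.3) / 77² = 96.8 / 5929 = 0.016327, an effective 61.25 independent breasts per arm.

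**Between arms (stated: 84% for 0.4 SD)**

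- SE of the difference = √(2 × 0.016327) = 0.1807; 0.4 / 0.1807 = 2.214; power = Φ(2.214 − 1.960) = **60.0%**.
- A 20,000-run simulation with cluster-robust variance gives 61%.
- Clustering ignored (ρ = 0): SE = √(2/77) = 0.1612; power 69.9%, or 79.9% one-sided at 5%. With SD taken as that of the analysed variable, no non-negative correlation between breasts reaches 84%.
- 84% power needs (1.960 + 0.994) × 0.1807 = **0.53 SD**. At 0.4 SD it needs an effective 109.1 breasts per arm, which is 109.1 / 61.25 × 44 = 78.4, so about 79 women per arm.
- If SD means the raw-score SD, multiply the variance by 1 − r² (baseline-adjusted regression) or by 2(1 − r) (change score), where r is the baseline to month-12 correlation. The only between-time value in the power text is 0.3 (16.2.2.1). It gives 64% and 46% respectively. Reaching 84% needs r of about 0.66 or 0.72.

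**Within arm (stated: 90% for 0.3 SD)**

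With raw-score SD, each breast's change has variance 2(1 − 0.3) = 1.4 SD², and the covariance of the two breasts' changes is 2(0.3 − c), where c is the cross-breast, cross-time correlation. So SE² = [77 × 1.4 + 66 × 2(0.3 − c)] / 77². The plan gives no separate c. The values 0.09 (= 0.3 × 0.3) and 0 are assumptions that show the range.

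| Reading | SE | Power at 0.3 SD | Effect for 90% power |
|---|---|---|---|
| SD of the change, correlation 0.3 between breasts | 0.1278 | 65.1% | 0.41 SD |
| Raw-score SD, all correlations 0.3 | 0.1348 | 60.4% | 0.44 SD |
| Raw-score SD, c = 0.09 | 0.1512 | 51.0% | 0.49 SD |
| Raw-score SD, c = 0 | 0.1577 | 47.7% | 0.51 SD |

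- One-sided 5% would give 60–76% across these rows.
- With SD of the change and clustering ignored: SE = 1/√77 = 0.1140; power 74.9% two-sided, 83.8% one-sided.
- With raw-score SD, 90% needs a between-time correlation of about 0.67 (c = 0.3) to 0.74 (c = 0.3r), against the stated 0.3.

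**Attempts to recover the stated figures.** One-sided alpha of 10% gives 82% between arms, against the stated 84%. Multiplying the variance by (1 − 0.3) instead of inflating it gives 84.3% between arms and 88.2% within an arm. Pooling both arms gives 91.3% (SD of the change) or 88.2% (raw-score SD, all correlations 0.3) for the paired test, against the stated 90%. The plan describes none of these, and their origin cannot be settled from the documents.

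**Primary power for reference.** 90% versus 60% atypia with 44 per arm (16.2.1.1) gives 91.5%, against 90% stated.

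**The case against.** The best defence of the 84% is that raw-score SD and the covariate-adjusted regression were intended. Adjustment could then supply the missing precision, and it need not all come from baseline score because age, race and prior excisional biopsy are also in the model. The covariates together would have to explain about 44% of the outcome variance (0.66² ≈ 0.44). That is possible, but the plan states no such assumption, and the stated t-test and alpha belong to the unadjusted comparison.

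For the within-arm figure, the simplest reading of the correlation statement is a common 0.3 within each woman, so 60–65% is better grounded than the 48–51% that rests on assumed cross-correlations. That is fair. The lower values are sensitivity cases. It is also fair that the alpha is assumed and that the 75% bound applies to SD of the change at two-sided 5%. One-sided 5% narrows the gap to 14–30 points but does not close it.

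Pooling the arms would come close to 90%, but the section says the analyses are done for each arm.

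Finally, the consequence is limited: one analysis is exploratory, the arms are compared only descriptively in the other, and no decision rule uses either figure. That bears on the weight of the point, not on its correctness.

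**Conclusion.** The concern holds. Neither stated power follows from the plan's inputs.

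- **Between arms:** about 60% rather than 84% for 0.4 SD, a gap of 24 points. This takes SD as that of the analysed variable. Under raw-score SD with the 0.3 between-time correlation, the figure is 46–64%.
- **Within arm:** about 48–65% rather than 90% for 0.3 SD, a gap of 25–42 points, at an assumed two-sided 5%. The better-grounded readings give 60–65%.

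Reaching the stated powers needs a correlation that the plan does not state (about 0.66–0.74), a looser alpha, pooled arms, or a variance factor applied in the wrong direction. This should be corrected, but it does not touch the sample size or the primary analysis.

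**What to change.** - **Section 16.2.1.2:** say which SD is meant. For SD of the analysed variable, restate as about 60% power for 0.4 SD, or 84% power for about 0.53 SD. If raw-score SD with covariate adjustment was intended, state the assumed baseline to month-12 correlation (or the variance explained by all covariates) and recompute.
- **Section 16.2.2.1:** state the alpha, the SD and the full correlation structure, including the correlation between one breast at month 0 and the other at month 12. Then give the per-arm power and detectable effect from the matching row of the table above.

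Deleting the two power figures would also remove the error, though with less information for the reader. The cost is wording in two paragraphs and less favourable stated powers. Sample size, tests and primary power stay as they are.

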#### 16.2.2 Secondary Objectives:

# 16.2.2.1 Test for Masood score and the presence of atypia or disappearance of atypia in RPFNA after 12 (for both arms) and 24 months for Metformin arm:

We will investigate the trend of Masood score and presence of atypia measured at month 0 and 12 for metformin arm and placebo arm. Breasts will be the sampling units in the analysis of Masood score, while either women (in the primary analysis) or breasts (in the secondary analysis) will be regarded as sampling units in the analysis of atypia. At first, we will perform descriptive analyses for summary statistics of Masood score and atypia at each measurement time. We will also generate a line plot connecting the Masood scores of each breast over time to investigate the time trend.

We will compare the mean Masood scores between 0 vs. month 12 using paired ttests. In this analysis, we will use the breasts as sampling units. The possible dependency between data points from two breasts of each woman will be adjusted using the GEE method using the working independent correlation model. Assuming that about 25% of women (n=11) will contribute one breast and the remaining 75% of women (n=33) will contribute samples from both breasts for each arm, we will have 90% of statistical power to detect a difference of 0.3 times SD if the intracluster correlation coefficients between breasts and two time points are 0.3 for each woman. We will conduct McNemar test to compare the proportion of atypia between month 0 and month 12. These analyses will be conducted for each arm, and the results will be descriptively compared between two arms. We will summarize the 24-month data for the metformin arm.

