#### **16.2.1.2 Exploratory Analysis**

An exploratory analysis will be conducted using the breasts as sampling units, not women, so that all eligible breasts of eligible patients will be included in data analysis. The variance of the test statistic for comparing the presence of atypia at month 12 will be estimated using the generalized estimating equation (GEE) approach to account for the possible dependency among the binary atypia observations from each patient.

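### Section 16.2.2.1 attaches no adjustment for paired breasts to its breast-level McNemar test of atypia at month 0 versus month 12, so that p-value is not guaranteed valid (minor)

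*Combined protocol and SAP*

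**What the plan says.** Section 16.2.2.1 sets the units for atypia as follows: "either women (in the primary analysis) or breasts (in the secondary analysis) will be regarded as sampling units in the analysis of atypia". The one test it names for atypia over time is "We will conduct McNemar test to compare the proportion of atypia between month 0 and month 12". It runs in each arm separately, and the arms are then compared only descriptively. The sentence does not name its unit, a variance method, or a continuity-corrected or exact version. No confidence interval is planned for it.

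Earlier in the same paragraph stands "The possible dependency between data points from two breasts of each woman will be adjusted using the GEE method". That sentence follows the paired t-tests of mean Masood score and is tied to them by its reference to the analysis just described. The McNemar sentence comes later, after a power statement for mean scores.

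Other breast-level comparisons carry an explicit adjustment. For binary atypia between arms, Section 16.2.1.2 uses a GEE variance "to account for the possible dependency among the binary atypia observations from each patient". For the continuous score in the same section, "the variances of t-test (in univariate analysis) and regression estimates (in multivariate analysis) will be estimated using the GEE". Section 16.2.2.4 uses GEE for the breast-level analyses of RPPM values.

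On layout, Section 16.2.1.2 states that "there will be about 77 (= 11x1 + 33x2) data points (breasts) per arm in this analysis".

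**The concern.** McNemar's statistic divides the difference between the two discordant counts by the square root of their sum. That variance is correct when the pairs are independent. Here a pair is one breast at two visits, and most women supply two such pairs. A woman's two breasts share the woman, her treatment and her visits, so their changes may be correlated. If the correlation is positive, the ordinary standard error is too small and the test rejects too often. If it is negative, the test is conservative.

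A programmer who followed the McNemar sentence as written would run the ordinary test on about 77 breasts from 44 women per arm. The plan corrects for this dependency in the neighbouring analyses, so the gap looks like an omission. At stake is the p-value for change within each arm in the breast-level version.

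**Working it through.** **Inputs.** Section 16.2.1.2 gives 11 women with one breast and 33 with two, per arm. The count reproduces: 11 × 1 + 33 × 2 = 77. No alpha is stated for the McNemar test; two-sided 5% is assumed. The plan gives no power or error rate for this test, so it has no figure of its own to reproduce.

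**Formula.** Let ρ be the correlation between a woman's two within-breast changes in atypia. When there is no average change, the variance of the summed changes is inflated, relative to McNemar's, by

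DE = 1 + ρ × Σm(m−1)/Σm = 1 + ρ × (33 × 2)/77 = 1 + 0.857ρ.

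The true two-sided error of a nominal 5% test without continuity correction is 2 × [1 − Φ(1.96/√DE)].

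| ρ (assumed) | DE | √DE | 1.96/√DE | True type I error |
|---|---|---|---|---|
| −0.1 | 0.914 | 0.956 | 2.05 | 4% |
| 0 | 1.000 | 1.000 | 1.96 | 5% |
| 0.1 | 1.086 | 1.042 | 1.88 | 6% |
| 0.3 | 1.257 | 1.121 | 1.75 | 8% |
| 0.5 | 1.429 | 1.195 | 1.64 | 10% |

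At ρ = 0.3 the true standard error is 12% larger than the one McNemar uses, and 77 breasts carry the information of 77/1.257 ≈ 61.

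**What the documents say about ρ.** They do not give it. Section 16.2.1.2 has "Assuming that the intracluster correlation coefficient between two breasts is 0.3", but for the continuous Masood score. Section 16.2.2.1 assumes 0.3 between breasts and between time points, and leaves open the correlation between one breast at month 0 and the other at month 12. With equal variances,

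ρ = (between-breast correlation − cross-breast, cross-time correlation)/(1 − between-time correlation).

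If all three are 0.3, ρ = (0.3 − 0.3)/0.7 = 0 and the ordinary test is correct. If the cross term is 0.09, ρ = 0.21/0.7 = 0.3 on the score scale.

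**Simulation.** Binary atypia was generated by cutting correlated normal scores, with 44 women per arm in the plan's layout, no true change, atypia prevalence 0.5 to 0.85, and 20,000 trials per scenario. Correlations refer to the underlying scores.

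| Scenario | Ordinary McNemar type I error |
|---|---|
| All correlations 0.3 | 5.0–5.4% |
| Between-breast and between-time 0.3, cross term 0–0.09 | 6.4–7.7% |
| Between-breast 0.5–0.6 | 7.7–9.6% |

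Across all scenarios a continuity-corrected McNemar test gave 2.5–6.3%, and a version summing changes within each woman gave 4.8–5.3%.

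A separate simulation imposed entry on at least one atypical breast, with no shared woman-by-time effect. The correlation of changes was then −0.06 to −0.16, and the ordinary standard error was 3–7% too large.

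**Woman-level version.** Section 3.3.1 requires atypia (Masood 14–17) for randomization. Section 16.2.1.1 classes a woman as having atypia if either breast does. Apart from any woman whose averaged baseline score falls below 14, every woman is therefore positive at month 0. The cell for gain of atypia is empty by design, and woman-level change can go only one way.

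**The case against.** The strongest reply is that the text never says breasts are treated as independent; that is inferred from silence. Section 16.2.1.2 already commits to GEE for breast-level binary atypia, so the intention is fairly plain. This stands as a limit on the wording. The claim is that no adjustment is specified, not that the sponsor has chosen to ignore the pairing.

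A reader might go further and infer that the p-values are wrong, or that the test is anti-conservative. The documents do not support this. The correlation of binary changes is not given. Section 1.3.2 reports no high degree of agreement between breasts, and Section 16.2.2.2 expects no left-right concordance. One literal reading of the 0.3 assumptions gives no inflation, and selection on baseline atypia can make the correlation negative. A reader might also infer faulty confidence intervals, but none are planned for this test. Nor is this the plan's only unadjusted analysis of clustered data: the ANOVA on RPPM duplicates in Section 16.2.2.3 states no woman-level adjustment either.

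The practical effect may also be small. Section 16.1.1 expects atypia to disappear in 40% of the metformin arm, or 0.4 × 44 ≈ 18 women, hence at least 18 breast losses. With 0 to 3 gains (assumed), z runs from 18/√18 = 4.2 to 15/√21 = 3.3. Dividing by 1.121 gives 3.8 to 2.9, still p < 0.005. That bears on one expected result, not on the validity of the test.

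Finally, regression to the mean after selection on atypia may matter more to any month 0 versus month 12 test. That is fair, and clustering the variance does not remove it.

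**Conclusion.** The point holds as a minor one. As written, Section 16.2.2.1 leads to an independence-based test on about 77 breasts from 44 women per arm, and the nominal 5% level is not assured. Over assumed correlations of changes from −0.1 to 0.5, true type I error runs from about 4% to about 10%. It is 5% if the changes are uncorrelated. These figures assume the plan's 11/33 layout, a two-sided 5% level and no continuity correction. A continuity correction would remove much of any excess.

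The consequence is confined to the secondary version of a within-arm secondary analysis. The primary endpoint and the sample size are untouched.

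It would be tempting to conclude that the woman-level McNemar test is the sound alternative. Clustering does not affect it, but entry on atypia makes its gain cell essentially empty, so it should not be presented as a meaningful two-way comparison.

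**What to change.** In Section 16.2.2.1, name the unit in the McNemar sentence. State that the breast-level month 0 versus month 12 comparison of atypia uses a clustered McNemar test, or a GEE model of atypia on time with working independence and robust variance clustered on woman. Either allows for a correlation of either sign.

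For women as units, replace the McNemar test with the proportion in each arm whose atypia has disappeared at month 12, with its confidence interval.

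The cost is a sentence or two of text. The GEE code is already needed for the neighbouring analyses, and no new data or sample size change is required.
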